## **IX. Safety Analyses**

Safety analyses will use data from the SS.

### **A. Adverse Events**

All subjects will be assessed regularly for potential occurrence of adverse events (AE) from the treatment period until the subject is off study. The Medical Dictionary for Regulatory Activities (MedDRA; Version 16.1) will be used to code all adverse events to a System Organ Class (SOC) and Preferred Term (PT). The incidence of treatment-emergent AEs (TEAE) will be summarized and tabulated by treatment group. A TEAE is defined as any AE that occurs on or after the date of first transfusion.

The National Cancer Institute Common Terminology Criteria for Adverse Events (version 4.03; CTCAE) will be used to grade severity of all AEs. The severity of each AE will be assessed as mild, moderate, severe, life-threatening or fatal. Several occurrences of the same AE in one subject will be counted once and the one with worst severity will be counted.

The relationship of each AE to the study treatment or to study procedure will be grouped as related or unrelated. Any AE with a CRF description of definitely related, probably related, or possibly related will be considered related. Any AE

with a CRF description of not related will be considered unrelated. Several occurrences of the same AE in one subject will be counted once and the one with the closest relationship to study treatment or to study procedure will be counted. If an AE is missing the relationship to study medication, the event will be assumed to be related for analysis and summarization.

The number and percentage of patients reporting each PT will be summarized by the treatment received in the period of onset. Incidence of AEs by maximum reported CTCAE grade will also be tabulated within each arm. The SAEs and AEs leading to study discontinuation will be displayed. The following summaries will be presented:

- Overall summary of TEAEs
- TEAEs by SOC and PT. The number and percentage of subjects with at least one TEAE, as classified by system organ class (SOC) and preferred term (PT), will be summarized by treatment received in the period of onset. For these summaries, subjects with multiple events will be counted only once per SOC and preferred term.
- Study Treatment-related TEAEs by SOC and PT
- Study Procedure-related TEAEs by SOC and PT
- TEAEs by maximum CTCAE grade, SOC and PT
- Serious TEAEs by SOC and PT
- UADEs by SOC and PT
- Adverse transfusion reactions
- TEAEs causing discontinuation from the study
- All-cause mortality
- Incidence of treatment-emergent antibody with confirmed specificity to RBCs derived from Mirasol-treated WB

Because all AEs will be recorded from the time of the first study-related transfusion through the end of study treatment follow-up visit or early termination, any AEs will by definition be TEAEs. However, causation by treatment may not be determined for AEs observed at the final follow-up visit due to off protocol transfusions administered since last study transfusion

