10 INVESTIGATIONAL PLAN

10.1 Study Design

[figure not shown]
This is a prospective, multi-center, randomized, crossover trial to evaluate the clinical effectiveness of MIR RBCs versus REF RBCs in transfusion dependent thalassemia patients. Throughout the clinical trial, RBC transfusion volume and frequency will be determined by each subject's treating physician.

Eligible subjects who have signed an informed consent form (ICF)/parental consent form and assent form, where applicable, will be enrolled and randomized 1:1 to a treatment sequence via an electronic system using a permuted-block schedule stratified by investigational site. Subjects will be randomized to receive either MIR RBCs followed by conventional RBCs, or to receive conventional RBCs followed by MIR RBCs.

The crossover trial design will consist of 2 treatment periods. Each period will include a 50 day wash-in phase (Day 0 of the wash-in = Day 0 of the treatment period) followed by 2 transfusion episodes for assessment of the primary endpoint. The 50-day wash-in serves to ensure that an adequate volume of RBCs from the assigned treatment allocation (MIR RBCs versus REF RBCs) have been transfused into the subject prior to collecting samples to support the primary endpoint.

Blood transfusion is the mainstay of care for individuals with thalassemia major. The purpose of transfusion is twofold: to improve the anemia and to suppress the ineffective erythropoiesis. A transfusion episode for these thalassemia patients are the routine transfusions administered on a regulator schedule for the life of the patient. An end of study treatment follow-up visit will occur 2-4 weeks after the last per protocol transfusion, prior to the next standard of care transfusion. A final study visit will occur at least 60 days after the last per protocol transfusion.

Figure 10-1: Study Schematic

During each treatment period, blood samples will be collected for safety and efficacy analysis.

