16.2.2.2 HLA Antibody Testing

A central laboratory will conduct HLA antibody testing. Samples will be collected from all subjects prior to each transfusion in Period 1 only, since 1 full treatment period will be adequate to assess chronic transfusions and will incorporate both study treatments (MIR RBCs and REF RBCs). Samples will be processed, stored, and shipped according to the instructions specified in the MOP.

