21.9 Safety Analyses

21.9.1 Adverse Events

The Medical Dictionary for Regulatory Activities (MedDRA) version 18.0 or later will be used to code all adverse events to a system organ class (SOC) and a preferred term (PT) within the SOC. The National Cancer Institute Common Terminology Criteria for Adverse Events (version 4.03; CTCAE) will be used to grade severity of all AEs.

The number and percentage of patients reporting each PT will be summarized by the treatment received in the period of onset. Incidence of AEs by maximum reported CTCAE grade will also be tabulated within each arm. The SAEs and AEs leading to study discontinuation will be displayed. The following summaries will be presented:

- Overall TEAEs
- Treatment-related TEAEs
- Adverse transfusion reactions
- TEAEs by maximum CTCAE grade
- SAEs and UADEs
- TEAEs causing discontinuation from the study
- All cause mortality
- Incidence of treatment-emergent antibody with confirmed specificity to RBCs derived from Mirasol-treated WB

Because all AEs will be recorded from the time of the first study related transfusion through the end of study treatment follow-up visit or early termination, any AEs will by definition be TEAEs. However, causation by treatment may not be determined for AEs observed at the final follow-up visit due to off protocol transfusions administered since last study transfusion.

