## IV. Study Design

### A. Design Overview

This is a prospective, multi-center, randomized, crossover trial to evaluate the clinical effectiveness of RBCs derived from Mirasol-treated WB (MIR RBCs) versus conventional RBCs (REF RBCs) in transfusion dependent thalassemia patients. Throughout the clinical trial, RBC transfusion volume and frequency will be determined by each subject's treating physician.

Eligible subjects who have signed an informed consent form (ICF)/parental consent form and assent form, where applicable, will be enrolled and randomized 1:1 to a treatment sequence via an electronic system using a permuted-block schedule stratified by investigational site. Subjects will be randomized to receive either MIR RBCs followed by REF RBCs, or to receive REF RBCs followed by MIR RBCs.

The crossover trial design will consist of 2 treatment periods. Each period will include a 50-day wash-in phase (Day 0 of the wash-in = Day 0 of the treatment period) followed by 2 transfusion episodes for assessment of the primary endpoint. The 50-day wash-in serves to ensure that an adequate volume of RBCs from the assigned treatment allocation (MIR RBCs versus REF RBCs) have been transfused into the subject prior to collecting samples to support the primary endpoint.

An end of study treatment follow-up visit will occur 2-4 weeks after the last per protocol transfusion, which should coincide with the next standard of care transfusion. A final study visit will occur at least 60 days after the last per protocol transfusion.

During each treatment period, blood samples will be collected for safety and efficacy analysis.

Blinding is not feasible because riboflavin used in the Mirasol-treated WB may cause yellow colored urine in transfusion recipients of Mirasol-treated blood products. Also, there is a difference in MIR RBC and REF RBC storage bags and labels. However, subjects, investigational site staff, and the Sponsor will not be informed of the randomization assignment. Study team members conducting safety assessments on subjects should remain blinded, whenever possible, to ensure causality determination remains unbiased. Central and Local Blood Centers will be informed of the randomization assignment to provide study product for transfusion.

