#### Treatment Start Date

Treatment start date is defined within each period as the date of the first transfusion received for each period.

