#### **Safety Set (SS)**

The Safety Set (SS) will include all randomized patients who undergo at least 1 episode of treatment after randomization. Patients will be analyzed according to the actual treatment received (MIR RBCs, REF RBCs) within each period. If a patient receives MIR RBCs at any time during a given period, patients will be summarized in the SS as receiving MIR RBCs for

that period. If a patient randomized to receive RBCs derived from Mirasol-treated WB only receives untreated RBCs within a given period, the patient will be summarized in the SS as receiving RBCs from untreated WB for that period. The safety analysis set will be used in reporting the safety issues in the study.

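### Adverse events are assigned to the product of the period of onset with no lag, which dilutes the Mirasol-versus-conventional comparison for delayed or cell-dependent events; add Period 1 and post-Day 50 tables

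*SAP*

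**What the plan says.** The attribution rule is the same in both documents. SAP IX.A has "The number and percentage of patients reporting each PT will be summarized by the treatment received in the period of onset", and Protocol 21.9.1 also has events "summarized by the treatment received in the period of onset".

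Three definitions fix when a period starts to collect events:

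- SAP VI.A: "Treatment start date is defined within each period as the date of the first transfusion received for each period".
- SAP IV.A: "Each period will include a 50-day wash-in phase (Day 0 of the wash-in = Day 0 of the treatment period"), so the wash-in is the opening part of the new period and not a gap between periods.
- SAP IX.A: "A TEAE is defined as any AE that occurs on or after the date of first transfusion", so events during the wash-in are included.

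The Safety Set rule in SAP VI.I looks at units given in the period. It classes a period as Mirasol with the condition "If a patient receives MIR RBCs at any time during a given period". Mirasol cells left over from the previous period do not move an event out of the conventional column.

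Post-baseline tables are by treatment (SAP VI.K). The list in SAP IX.A has no adverse event table by period, by sequence or for Period 1 alone. Its only caveat about attributing events to a product concerns the final follow-up visit.

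**The concern.** Comparing safety between products is part of the secondary objective (Protocol 7.2, SAP II.B). Transfusion-dependent patients cannot have a physical washout, so each period opens with a mixed circulation. An event that depends on circulating Mirasol cells, or on late immune exposure to them, and that begins after the switch to conventional units is counted as conventional. In every Mirasol period, the early weeks are counted as Mirasol while much of the circulation is still conventional. Both errors push the two columns toward each other, so a real difference would look smaller.

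Other parts of the plan are arranged so that this matters less. For efficacy, Protocol 10.1 says: "The 50-day wash-in serves to ensure that an adequate volume of RBCs from the assigned treatment allocation" has been given before endpoint sampling, and SAP VIII.B tests for carryover. For HLA antibodies, Protocol 16.2.2.2 says: "Samples will be collected from all subjects prior to each transfusion in Period 1 only". Adverse events have no comparable arrangement.

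**Working it through.** The documents give no figure for the adverse event comparison, so there is none to reproduce. The check is a model of the circulating cell mix.

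**Inputs from the documents**
- Linear survival L: 60.49 days Mirasol (SD 5.6), 81.57 days untreated (Protocol 5.2, Table 19-3; healthy volunteers, autologous cells).
- Mean recovery R: 82.5% Mirasol, 91.7% untreated (Protocol 19.3.3).
- Transfusion interval i: 14 to 28 days (Protocol 11.2).
- Period: 50-day wash-in, then two transfusion episodes (Protocol 10.1).

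**Assumptions**
- Equal volumes and no endogenous red cells.
- The first unit of the new product comes one interval after the last unit of the old.
- Event risk is proportional to cell share, and the true rate ratio is 2.0.

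**1. Survival model.** The fraction surviving at age a is R × (1 − a/L), and zero after L. As a check, half of the infused cells remain at L × (1 − 0.5/R). This gives 60.49 × (1 − 0.5/0.825) = 23.8 days and 81.57 × (1 − 0.5/0.917) = 37.1 days. Table 19-3 gives half-lives of 22.58 and 35.83 days, so the model is close.

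**2. Period length.** (50/i rounded up, plus 2) × i = 6 × 14 = 84, 5 × 21 = 105 and 4 × 28 = 112 days.

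**3. Last Mirasol cells in a conventional period after Mirasol.** 60.49 − i = day 46, 39 or 32, which is 55%, 38% or 29% of the period.

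**4. Mirasol share just after the first conventional transfusion.** At 21 days, the surviving Mirasol cells are aged 21 and 42 days: 0.825 × (1 − 21/60.49) + 0.825 × (1 − 42/60.49) = 0.539 + 0.252 = 0.791. The share is 0.791/(0.791 + 0.917) = 46%. The same sum gives 1.391/2.308 = 60% at 14 days and 0.504/1.421 = 35% at 28 days.

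**5. Mean shares and the ratio the tables would show.** Let g be the mean Mirasol share over a Mirasol period. Let f be the mean Mirasol share over all conventional time, which is half the Period 2 figure because only one sequence is affected. For a true ratio of 2.0 the table shows (1 + g)/(1 + f).

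| Interval (days) | 14 | 21 | 28 |
|---|---|---|---|
| Mirasol share, Period 2 conventional | 14.7% | 8.9% | 6.1% |
| f, all conventional time | 7.3% | 4.5% | 3.0% |
| Conventional share of a Mirasol period, 1 − g | 27.0% | 18.5% | 14.5% |
| Planned table, (1 + g)/(1 + f) | 1.730/1.073 = 1.61 | 1.815/1.045 = 1.74 | 1.855/1.030 = 1.80 |
| Period 1 only, f = 0 | 1.73 | 1.82 | 1.86 |
| Onsets after Day 50, f = 0 and g = 0.971/0.991/0.998 | 1.97 | 1.99 | 2.00 |

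For an assumed true ratio of 1.5 the planned table shows 1.32/1.38/1.41; for 3.0 it shows 2.15/2.42/2.56.

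**6. The two sources apart, true ratio 2.0.** Mirasol cells in conventional time alone give 2/1.073 = 1.86, 2/1.045 = 1.91 and 2/1.030 = 1.94. Conventional cells in Mirasol time alone give the Period 1 row. The second source is the larger.

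**The case against.** The strongest reply is that period-of-onset attribution suits most of the events that matter. Acute reactions follow the unit given that day. Protocol Table 19-1 puts delayed haemolytic reactions at 2 to 14 days, so with intervals of 14 to 28 days they mostly begin before the switch. HLA data come from Period 1 only. Mirasol-specific antibodies are reported by interval of detection (SAP IX.F). Bilirubin and LDH enter shift tables at each timepoint (SAP IX.B). The adverse event tables carry no test or margin, and the listings let a reader trace early Period 2 events by hand. All of this stands. It confines the point to later, cell-dependent or immune events and to how the tables are read.

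Several stronger readings are tempting but not supported:

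- *Mirasol cells contaminate 29 to 55% of the conventional period.* That counts any day with any surviving cell. The mean share is 6 to 15% of that period. If any residual cell carried full risk, this source alone would reduce 2.0 to 1.57 to 1.75, but nothing in the documents suggests such a rule.
- *Mirasol cells might last much longer, say 85 days.* That is (85 − 60.49)/5.6 = 4.4 SD above the reported mean, and above the 81.57 days of untreated cells.
- *Period 1 is free of carry-over, with a conventional arm never exposed to Mirasol.* Pre-study conventional cells dilute the Mirasol arm of Period 1 as well. Exclusion 14 bars pathogen-reduced red cells only for the previous 120 days.
- *The plan itself states that old cells must be discounted.* The wash-in is justified by the volume of assigned product given, and Period 1 HLA sampling by one period being adequate to assess chronic transfusion while covering both products. Neither rationale is stated as carry-over.

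**Conclusion.** The point holds for delayed, cell-dependent or immune events. Under the planned rule, an assumed true ratio of 2.0 would appear as about 1.6 to 1.8, with the greatest loss at 14-day intervals. The direction, toward no difference, follows from the attribution rule and the absence of a washout. The size rests on healthy-volunteer survival applied to thalassemia patients, equal volumes, no endogenous cells, and risk proportional to cell share. The model works with rates; percentages of patients with an event behave similarly only when events are uncommon.

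A reader should not infer that the safety comparison is invalid, or that a Period 1 difference must override the pooled table. The planned tables are descriptive and serve acute events well. They cannot show whether events in the conventional column cluster after Mirasol exposure. This is a cheap improvement to a stated secondary objective.

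**What to change.** In SAP IX.A keep the pooled tables and add, before database lock, the same tables for TEAEs, treatment-related TEAEs, SAEs and transfusion reactions in two restricted forms:

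- **Period 1 alone, by product received.** This is the randomised comparison without crossover carry-over from Mirasol into conventional time, immune carry-over included. The modelled ratio is 1.73 to 1.86, because pre-study conventional cells remain.
- **Onsets after Day 50 of each period, by product received.** The modelled ratio is 1.97 to 2.00 for events that follow the cell mix. This table does not remove immune effects that last from Period 1, so it complements the first. State which day count applies: the wash-in starts at Day 0, whereas SAP VI.A adds 1 to study days after the treatment start date.

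In the pooled tables, show Period 1 and Period 2 conventional events separately.

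No new data, procedure or sample size is needed. The cost is precision: about 97/2 ≈ 48 subjects per arm in the Period 1 tables and fewer events in both added sets, so wider intervals. The added tables should be labelled descriptive, like the existing ones.

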## **B. Clinical Laboratory Results**

All laboratory values will be converted to International System of Units (SI units).

Laboratory test covered by the CTCAE (version 4.03) will be assigned grades accordingly. A grade of 0 will be assumed for non-missing values not graded as 1 or higher. In the unlikely cases where a laboratory normal range overlaps in the higher (ie, non-zero) CTCAE grade, the laboratory value will still be taken as within normal limits and assigned a CTCAE grade of 0. Grade 5 will not be used.

For laboratory tests where grades are not defined by CTCAE, results will be graded by the low/normal/high classifications based on normal ranges.

The following summaries by treatment group will be presented separately for laboratory parameters: shift in CTCAE grade from pre-transfusion of wash-in period to each assessment timepoint for laboratory tests that are graded; for non-graded tests, shift in normal range classification from pre-transfusion of wash-in period to each assessment timepoint. For both shift tables, a summary of worst shift from pre-transfusion of wash-in period will be presented.

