21.2 Reporting Conventions and Definitions

Duration of events will be calculated in days as (stop date – start date + 1). Conversions to weeks, months, or years will be calculated as days/7, days/30.4375, or days/365.25, respectively.

For analysis purposes, baseline will be defined as the day of the first transfusion within each treatment period. In general, missing values will be handled as follows. For continuous variables at baseline, missing values will be excluded from calculation of summary statistics and the number and percent of patients with missing values will be displayed. For categorical values at baseline, the number and percent of patients with missing values will be displayed.

Summary tables of post-baseline measures will be presented by treatment:

- MIR RBCs: RBCs will be derived from WB collected in CPD solution, treated with the Mirasol System for WB, LR, and stored in AS-3 for \leq 21 days at 1 - 6°C
- REF RBCs: LR apheresis RBCs or WB-derived RBCs will be per site standard inventory

Patients will be randomized by treatment sequence: MIR RBCs followed by REF RBCs (MR) or REF RBCs followed by MIR RBCs (RM). Summary tables of baseline measures will be presented by treatment sequence.

Treatment start date is defined within each period as the date of the first transfusion received for each period.

Study day for analysis purposes is defined as (date of event – treatment start date) (+ 1 if the event occurs after treatment start date) within each period.

Baseline for analysis purposes is defined as the last assessment prior to treatment start date/time (or randomization date, for patients who never receive any treatment) for each treatment period. In cases where the date is the same and the times are unknown, assessments taken on the same day are considered baseline.

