21.9.2 Laboratory Tests

All laboratory values will be converted to International System of Units (SI units).

Laboratory test covered by the CTCAE (version 4.03) will be assigned grades accordingly. A grade of 0 will be assumed for non-missing values not graded as 1 or higher. In the unlikely cases where a laboratory normal range overlaps in the higher (ie, non-zero) CTCAE grade, the

laboratory value will still be taken as within normal limits and assigned a CTCAE grade of 0. Grade 5 will not be used.

For laboratory tests where grades are not defined by CTCAE, results will be graded by the low/normal/high classifications based on normal ranges.

The following summaries by treatment group will be presented separately for laboratory parameters: change from baseline to the time point prior to each transfusion and change from the pre transfusion time point between each consecutive transfusion.

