## **VI. General Analytical Considerations**

### **A. Study Time Points**

#### Baseline

Baseline for analysis purposes is defined as the last assessment prior to treatment start date/time (or randomization date, for patients who never receive any treatment) for each treatment period. In cases where the date is the same and the times are unknown, assessments taken on the same day are considered baseline.

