#### **C. Vital Signs**

Vital signs will be performed at baseline, during and within 15 min post-transfusion, 1 Day post-transfusion, and 7 Days post-transfusion. Vital signs include temperature, heart rate (HR), respiratory rate (RR), blood pressure (BP), and arterial oxygen saturation via pulse oximetry (SpO2), will be listed by treatment sequence, treatment group and time point. Vital signs will be summarized as actual and change from baseline for each treatment group at each scheduled assessment.

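### Laboratory shifts start from a baseline reset in each period with no off-product gap, so about half of the REF baselines follow Mirasol and the pooled REF column can mislead

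*SAP*

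**What the plan says.** SAP IX.B plans, by treatment group, "shift in CTCAE grade from pre-transfusion of wash-in period to each assessment timepoint for laboratory tests that are graded", the same for normal-range class where no grade exists, and a worst-shift summary. It does not say which period's wash-in is meant.

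The general definitions point to a reset in each period. SAP VI.A states: "Baseline for analysis purposes is defined as the last assessment prior to treatment start date/time", and its parenthesis continues "or randomization date, for patients who never receive any treatment) for each treatment period". It adds: "Treatment start date is defined within each period as the date of the first transfusion received for each period". Protocol 21.2 gives two baseline wordings, one being "baseline will be defined as the day of the first transfusion within each treatment period"; both are per period. The wash-in comes after that baseline, not before it: "Each period will include a 50-day wash-in phase (Day 0 of the wash-in = Day 0 of the treatment period" (SAP IV.A).

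Protocol 21.9.2 plans two laboratory summaries: "change from baseline to the time point prior to each transfusion", and the change between consecutive pre-transfusion values. The second does not use the period baseline, and SAP IX.B does not carry it over. SAP IX.B also lists no by-period table and no summary of actual laboratory values. For vital signs, SAP IX.C does plan actual values: "Vital signs will be summarized as actual and change from baseline for each treatment group at each scheduled assessment".

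**The concern.** The two products' columns do not start from the same background. Protocol 11.3 (exclusion 14) bars pathogen-reduced RBCs in the 120 days before entry, so every Period 1 baseline is on conventional blood. In the REF-then-MIR sequence the Mirasol baseline follows REF. Only the REF baseline in the MIR-then-REF sequence follows Mirasol.

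The protocol names reduced RBC survival as a Mirasol risk (19.3, 19.3.3), so a lasting effect on hemolysis markers is plausible. Bilirubin, LDH and haptoglobin are all collected (16.2.1). If such a marker has moved by the end of a Mirasol period, the moved value becomes the REF baseline. A later return to normal then counts as improvement on REF, and REF worsening is under-counted. The laboratory summaries planned in the SAP would not let a reader see this.

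**Working it through.** **Share of REF baselines taken on Mirasol.** The plan's number randomized reproduces: 77 / (1 − 0.20) = 96.25, rounded up to 97, or 97 / 2 = 48.5 per sequence. Every REF-then-MIR subject gives a REF baseline at entry. A MIR-then-REF subject gives one only on reaching Period 2.

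- No dropout in Period 1: 48.5 / 97 = 50%.
- Half of the 20% dropout in Period 1: 43.65 / (48.5 + 43.65) = 47%.
- All of it in Period 1: 38.8 / (48.5 + 38.8) = 44%.

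This is about 39 to 49 subjects.

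**Whether Mirasol cells are still circulating.** Inclusion criterion 1 gives 2–4 week intervals, and protocol 5.2 gives a mean linear survival of 60.49 days for Mirasol-treated cells in healthy volunteers. The fraction of the last Mirasol transfusion remaining is 1 − 14/60.49 = 77% at 14 days and 1 − 28/60.49 = 54% at 28 days. These are fractions of cells. The documents do not give the persistence of an effect on any analyte.

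**Mean change from baseline (protocol 21.9.2).** Let d be the Mirasol effect late in a period, p the fraction of d present at the Period 2 baseline, and r the fraction of that residual which reverses by late Period 2 on REF. Assume equal sequences and no time trend; p and r are assumptions, each from 0 to 1.

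- MIR, either period: +d.
- REF, Period 1: 0.
- REF, Period 2: (1 − r)pd − pd = −rpd.
- Pooled REF: −rpd/2. Contrast, MIR minus REF: d(1 + rp/2).

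If the Period 1 baseline were used throughout, REF in Period 2 would be (1 − r)pd and the contrast d(1 − (1 − r)p/2). In a Period 1-only comparison the contrast is d whatever p and r are.

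| p | r | Period baseline | Period 1 baseline | Period 1 only |
|---|---|---|---|---|
| 0 | any | d | d | d |
| 0.5 | 1 | 1.25d | d | d |
| 1 | 1 | 1.5d | d | d |
| 1 | 0.5 | 1.25d | 0.75d | d |
| 1 | 0 | d | 0.5d | d |

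With 44% rather than 50% of REF baselines on Mirasol, the largest overstatement falls from 50% to 44%.

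For values drawn just before a transfusion, p is close to 1 by construction. Chemistry is drawn within 1 hour before transfusion (protocol 14.3.1), and the schedule shows no visit between periods, so the Period 2 baseline is in effect the last Mirasol on-treatment value. For those values d is already only what survives 2–4 weeks, and may be zero.

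**Shift tables (SAP IX.B).** As an illustration only, take a latent normal analyte with between-subject SD 0.8 and residual SD 0.6 (total SD 1), a grading threshold at 1 SD, d = 0.5 SD and full reversal on REF. Simulated worsening is 19% in the Mirasol column at every p. Pooled REF worsening is 8.1% at p = 0, 7.2% at p = 0.5 and 6.4% at p = 1. Splitting by sequence exposes this: at p = 1, REF worsening is 8.3% in Period 1 and 4.5% in Period 2, and REF improvement is 8.2% and 19.6%.

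**The case against.** The case for leaving the plan alone is substantial. SAP IX.B plans categorical shifts, so a bias in mean change does not describe its tables. In the illustration the pooled REF figure moves by less than two percentage points even at full persistence. The 50% figure needs the whole effect to last to the Period 2 baseline and then to vanish. With reversal the bias runs against Mirasol, the cautious direction for safety. Laboratory abnormalities that are treated, clinically significant or judged related are also recorded as AEs (protocol 19.5.1) and summarized by treatment in the period of onset (SAP IX.A).

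All of that stands, and it limits the size of the point. It does not remove it: for a persistent analyte the pooled REF column mixes two kinds of baseline, and the SAP omits the protocol summary that does not use the period baseline.

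A reader might go further and infer three things that the documents do not support.

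- Potassium and vital signs are distorted too. Protocol 19.3.2 calls hyperkalemia generally transient. Nothing suggests a vital-sign effect lasting 2–4 weeks, and actual vital signs are summarized.
- Abnormalities arising on Mirasol are hidden. They are counted in the Mirasol column, whose baselines are all on conventional blood. Not counting a persisting one again under REF is correct attribution.
- The Period 1 value should be the baseline for both periods. If the effect does not reverse, that turns a correct contrast of d into d/2 and credits Mirasol effects to REF.

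**Conclusion.** The concern holds in a limited, conditional form. On the natural reading of SAP IX.B, about 44–50% of REF baselines follow Mirasol and no Mirasol baseline does. Where an effect is present before the next transfusion and then reverses on REF, a mean change contrast is overstated by 0–50%, and REF worsening in the shift tables is understated. If nothing persists, or nothing reverses, the contrast is not biased by the baseline. The documents give neither persistence nor reversal for any analyte, so an unconditional 50% overstatement cannot be claimed. Hemolysis markers are the plausible case, by inference from reduced RBC survival. Severity is minor: the summaries are descriptive, carry no test or decision rule, and laboratory shifts are not among the listed safety endpoints (SAP III.B).

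**What to change.** In SAP IX.B:

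1. State that the reference value is the one before the first transfusion of each period's own wash-in.
2. Present the shift and worst-shift tables by sequence and period as well as pooled. Name the Period 1 MIR versus REF comparison as the uncontaminated reading: it is randomized, and all its baselines are on conventional RBCs.
3. Add actual laboratory values by treatment and period.
4. Restore the protocol 21.9.2 summary of change between consecutive pre-transfusion values.

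Keep the period baseline. A table from the pre-Period 1 value may be added as a supplement at most, with a note that it attributes persisting Mirasol effects to REF in Period 2.

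The cost is SAP wording and extra table shells, with no new data. The Period 1 comparison uses about half of the observations and is between subjects, so it is less precise; it supplements the pooled tables and does not replace them.
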